10.2.5. Follow-up

Once participation in this extension trial is completed, there will be no follow-up visit except as required to follow serious adverse event (SAEs) that are determined to be related to the investigational product (See Section 12.1.3).

11. ASSESSMENTS

11.1. VITAL SIGN MEASUREMENTS

Subject should rest for at least 5 minutes before assessment. For younger subjects for whom this may not be possible, attempts should be made to measure vital signs when subject is calm. The following vital signs should be measured:

- Heart Rate
- Blood Pressure
- Respiratory Rate
- Body Temperature

11.2. WEIGHT MEASUREMENT

Weight should be measured at each visit by the same auxologist at approximately the same time of day on the same calibrated weight scale (to minimize bias and reduce variability). Subjects should be wearing light clothing and no shoes. For subjects who cannot stand independently, a calibrated pediatric/infant weight scale should be used.

11.3. HEIGHT MEASUREMENT

Height should be measured at each visit, preferably by the same auxologist, at approximately the same time of day using a wall-mounted stadiometer (to minimize bias and reduce variability), the accuracy of which has been verified prior to each visit using a validated metallic calibration rod.

Children < 2 years old should be measured in a recumbent position using a length board placed on a flat, stable surface such as a table. Note: despite previous height measurements being performed on a length board, once a subject is 2 years old, the subsequent measurements should be performed on a stadiometer.

For subjects \geq 2 years old, obtain the height measurement on a wall-mounted stadiometer following the general guidance below:

- The subject should not stretch prior to height determination

- The subject should be standing without shoes and socks. Thin foot covers over bare feet may be worn.
- The subject should be wearing only light clothing so that the subject's pose can be observed
- The subject's gaze should be forward and in a horizontal position (Frankfurt plane)
- The subject's heels should be placed together. If the subject has genu valgum (knock-knee), the knees must be in contact with each other and the heels as close to each other as possible
- The subject's heels, buttocks, shoulders, and occiput of the cranium should all be in contact with the stadiometer
- Upward pressure should be applied to the subject's mandibular rami (jaw)
- The subject's shoulders should be relaxed, and pressure applied to the abdomen to reduce lordosis (spine curvature)
- The counterweight head is lowered until it is in contact with the highest part of the subject's head
- The height measurement is read at the horizontal level with the counter to the nearest 0.1 cm
- The subject should step away from the stadiometer and **repeat the previous steps 2 more times**. Repeated determinations must be within 0.5 cm of each other otherwise three new measurements must be performed and recorded.

For subjects < 2 years old, obtain the height measurement on a length board following the general guidance below ([WHO, 2008](#)):

- The subject should be undressed (diaper/underwear is acceptable)
- The parent/legal guardian/caregiver or another individual should place the subject supine on the length board with the subject's head against the fixed headboard, compressing the hair
- The subject's head should be positioned so that an imaginary vertical line from the ear canal to the lower border of the eye socket is perpendicular to the board. The subject's eyes should be looking straight up
- The auxologist should stand on the side of the length board, clearly able to see the measuring tape. If possible, the subject's parent/legal guardian/caregiver or another individual should stand behind the headboard and hold the subject's head in position.
- The subject should lie straight along the board, with shoulders touching the board and without arching the spine
- The subject should not change position during measurement
- Gentle pressure should be applied to the subject's knees to straighten the legs as far as possible
- While the subject's knees are being held with one hand, the footboard should be pulled with the other hand until flat against the subject's feet, toes pointing upwards

- Measurement of the subject's length is read and recorded in centimeters to the last completed 0.1 cm

11.4. PHYSICAL EXAMINATION

A physical examination should be performed to include injection site examination to assess for local tolerability. **For subjects who were treated with Genotropin in the prior TransCon hGH CT-301 trial**, Visit 1 injection site examinations to the daily hGH treatment areas should be explicitly documented so as to differentiate from any new reactions that occur during the extension trial.

11.5. FUNDOSCOPY

A standard fundoscopy may be performed to rule out blurred disc margins as indicated by subject symptoms. Fundoscopy may be performed throughout the trial as needed at the investigator's discretion.

11.6. PREGNANCY TEST

Testing for hCG should be performed for female subjects of child-bearing potential. Subjects who are sexually active must use an effective form of contraception.

11.7. PATIENT-REPORTED OUTCOME MEASURES

All Patient-Reported Outcomes (including PQ, CSDS, and C&OS) used in this trial have been assessed for understanding by GHD patients and their parents/legal guardians/caregivers as intended by the Sponsor in a prior Cognitive Debriefing study per the **Guidance for Industry – Patient-Reported Outcome Measures: Use in Medical Product Development to Support Labeling Claims** (*Guidance for Industry, 2009*).

11.7.1. Preference Questionnaire

The Preference Questionnaire should only be completed for subjects who were treated with daily Genotropin in the prior TransCon hGH CT-301 trial. The parent/legal guardian/caregiver will complete the PQ-P, while the subject, if ≥ 9 years old at Visit 1, will complete the PQ-C.

The timing of the preference questionnaires is listed in [Section 10.2.2.1](#).

11.7.2. Child Sheehan Disability Scale

The CSDS is an adaptation of the Sheehan Disability Scale to assess impairment related to childhood anxiety on children and their parents (*Whiteside, 2009*). This measure is being adapted in this trial to assess impairment related to treatment burden on children and their parents/legal guardians/caregivers.

At Visit 1 for all subjects, the parent/legal guardian/caregiver will complete the CSDS-P, while the subject, if ≥ 9 years old, will complete the CSDS-C.

The timing of the questionnaires to be completed after Visit 1 is listed in [Section 10.2.2.1](#) and [Section 10.2.2.2](#).

11.7.3. Convenience & Overall Satisfaction Domains of the Treatment Satisfaction Questionnaire for Medication

The original 14-item Treatment Satisfaction Questionnaire for Medication (TSQM) Version 1.4 is a reliable and valid instrument to assess patients' satisfaction with medication, providing scores in four domains – Side Effects, Effectiveness, Convenience and Overall Satisfaction. In naturalistic studies, administering the TSQM with the Side Effects domain could provoke the physician to assess the presence or absence of adverse events in a way that is clinically atypical, carrying the potential to interfere with routine medical care. As a result, a TSQM-9, derived from the TSQM Version 1.4 but without the Side Effects domain was created (*Bharmal, 2009*). This measure is being adapted further for this trial with the removal of the Effectiveness domain since effectiveness of hGH is not subjective and will be assessed with objective measures in this and other trials evaluating TransCon hGH. Thus, only C&OS of the TSQM-9 will be used.

At Visit 1 for all subjects, the parent/legal guardian/caregiver will complete the C&OS-P. The timing of the questionnaires to be completed after Visit 1 is listed in Section 10.2.2.1 and Section 10.2.2.2.

11.7.4. Device Usability Questionnaire

The Device Usability Questionnaire will be administered during this trial to assess GH Auto-Injector comfort, ease-of-use, and safety from the point of view of the caregivers and subjects. The data will supplement the GH Auto-Injector ease-of-use and functionality data gathered from a previous phase 1 clinical trial (comparing TransCon hGH administered by GH Auto-Injector and by syringe/needle), as well as data gathered during the formative and summative usability studies conducted in the device design and development phases. The data will also be analyzed as part of this current trial's overall assessment of safety and efficacy.

The DUQ was designed for use by children and/or adults. It consists of eight statements that the subject or caregiver (ie, whomever is designated as the individual primarily responsible for preparing and performing the injection with the GH Auto-Injector) is asked to rank on a scale indicating level of agreement. The statements relate to the level of comfort, ease-of-use, and safety.

This timing of DUQ administration is outlined in Section 10.2.2.4.

11.8. SUBJECT DIARY

The subject diary will be provided to the subject/parent/legal guardian/caregiver at the clinic visits and should be completed weekly on the day of investigational product administration. The data captured within the subject diary includes:

- Date and time of administration
- Dose of investigational product
- Person preparing and giving injection
- Location of injection on subject's body
- Assessment of local tolerability

- Changes to medications or subject's health

The subject diary should be reviewed by trial staff at every trial visit as part of concomitant medication review, adverse event reporting and investigational product compliance.

11.9. BONE X-RAY

Documentation of a bone age x-ray performed within approximately the past 52 weeks with appropriate documentation may be acceptable to show open epiphyses. However, if subject's prior documented bone age was > 12.0 years, and the bone age x-ray was performed greater than 9 months prior to Visit 1, a bone age x-ray should be performed within approximately 4 weeks of Visit 1.

11.10. LABORATORY ASSESSMENTS

Blood will be collected at each visit for assessments as listed in the Schedule of Events (Section 18.2), and described in Section 10.2. The total blood volume collected in a 3-month period will be up to approximately 18 mL, and the total collected in a 6-month period will be up to approximately 30 mL.

Detailed blood sampling, processing and assaying of samples will be provided in the laboratory manual.

11.11. LOCAL TOLERABILITY ASSESSMENT

Local tolerability is defined as an injection site reaction deemed abnormal from those ordinarily observed in SC injections (including pain, intensity, or duration), and will be collected on an AE form, as appropriate. Between visits, local tolerability will be evaluated and documented by the subject/parent/legal guardian/caregiver in the subject diary.

At clinic visits, assessment of local tolerability will be performed by injection site examination by trial staff (documented as part of the physical exam), in conjunction with subject diary review.

11.11.1. Reporting Local Tolerability as an Adverse Event

For the purpose of this trial, injection site reactions should not be documented as AEs unless the reaction:

- impacts the subject's ability to perform daily activities, or
- requires medical therapy (not including prophylactic therapy)

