12. ADVERSE EVENTS, SERIOUS ADVERSE EVENTS, AND REPORTING

12.1. ADVERSE EVENTS

12.1.1. Definition

An AE is defined as any untoward medical occurrence in a clinical investigation subject administered a pharmaceutical product and which does not necessarily have a causal relationship with the treatment. An AE can therefore be any unfavorable and unintended sign, symptom, or

disease temporally associated with the use of a medicinal (investigational) product, whether or not related to that product. An AE can arise with any use (eg, in combination with another drug), route of administration, formulation, or dose, including an overdose.

Possible AEs associated with TransCon hGH are listed in the Investigator's Brochure or the accompanying Reference Safety Information. The adverse reactions associated with commercially available daily hGH-containing products that may or may not be observed with use of TransCon hGH are:

- Sudden death in pediatric patients with Prader-Willi syndrome; risk factors include morbid obesity, history of upper airway obstruction or sleep apnea, and unidentified respiratory infection
- Intracranial tumors, particularly meningiomas, in teenagers/young adults treated with brain irradiation as children
- Injection site reactions/rashes (as well as rare, generalized hypersensitivity reactions)
- Skin atrophy and lipoatrophy
- **Note:** Rotating the injection site (see Section 9.3) is expected to decrease the risk of skin atrophy or lipoatrophy.
- Headaches
- Glucose intolerance, including impaired glucose tolerance/impaired fasting glucose as well as overt diabetes mellitus
- Intracranial hypertension with papilledema, visual changes, headache, nausea, and/or vomiting
- Fluid retention manifested by edema, arthralgia, myalgia, nerve compression syndromes (including carpal tunnel syndrome/paresthesias)
- Hypothyroidism (central [secondary] hypothyroidism may first become clinically evident or worsen in patients with GHD during hGH treatment)
- Slipped capital femoral epiphysis (occurs more frequently in patients with endocrine disorders or in patients undergoing rapid growth)
- **Note:** Any subject with the onset of a limp or complaints of hip or knee pain should be carefully evaluated for a slipped capital femoral epiphysis.
- Progression of pre-existing scoliosis due to rapid growth (hGH has not been shown to increase the occurrence of scoliosis)

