8.7. Other Assessments

Other safety assessments include weight, pubertal status, fundoscopy and bone age.

Weight and pubertal status are measured at each visit. Summary tables will be produced for these assessments by visit.

Fundoscopy is measured during the end of study. A listing will be presented for fundoscopy at each visit.

Bone age and delay in bone age are measured annually. Summary of the change from baseline will be presented in tables. Listing will also be provided. for bone age and delay in bone age.

9. Efficacy Analyses

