9.4. Subgroup Analysis

Efficacy variables including annualized HV, HSDS and IGF-1 SDS, demographic and baseline characteristics and TEAE may also be summarized based on the following subgroups.

- Age (< 3 years, ≥ 3 to <6 years. [≥ 6 to <11 years for girls, ≥ 6 to <12 years for boys] and [≥ 11 years for girls, ≥ 12 years for boys])
- Gender
- Asian vs Non-Asian
- Tanner Stage
- US vs. Non-US

For US sites, subjects will be switched from syringe to auto-injector during the study. The following analysis will be repeated for US subjects for auto-injection:

- Exposure/compliance
- TEAEs
- Local Tolerability
- Anti-body (only the positive vs negative)
- Device related PROs

10. Pharmacodynamics Analyses

The Pharmacodynamic (PD) endpoint, Serum IGF-1 SDS will be collected at 5 days \pm 1 day post-dose. Listings will be generated for PD endpoints.

11. Patient-Reported Outcomes

All Patient-Reported Outcomes used in this trial have been assessed for understanding by GHD patients and their parents/legal guardians/caregivers as intended by the Sponsor in a prior Cognitive Debriefing study per the Guidance for Industry. Questionnaire are administered during the study. The following endpoints are also collected:

- Preference for TransCon hGH or commercially available daily hGH treatment
- Satisfaction with daily hGH and weekly TransCon hGH over time

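### Protocol 11.11.1 limits which injection site reactions become AEs without saying whether atrophy, lipoatrophy or nodules are covered, and the SAP plans no full-population table of local tolerability that would show them otherwise

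*Protocol*

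**What the plan says.** **The rule.** Protocol 11.11 sets the scope: "Local tolerability is defined as an injection site reaction deemed abnormal from those ordinarily observed in SC injections". Such findings "will be collected on an AE form, as appropriate". Section 11.11.1 then states that "injection site reactions should not be documented as AEs unless the reaction" meets one of two conditions: it affects daily activities, or it needs medical therapy other than prophylaxis.

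**The named risks.** Protocol 12.1.1 lists reactions known from daily hGH products. "Skin atrophy and lipoatrophy" is one bullet; injection site reactions and rashes are another. Nodules are not in that list. They appear only in Section 5.3, where the phase 2 paediatric summary reports that no nodules or lipoatrophy were seen.

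**What is collected.** Under Protocol 11.11 and the Schedule of Events, staff examine injection sites at every clinic visit. The diary (Protocol 11.8) includes a tolerability assessment with each weekly injection. For former Genotropin subjects, Protocol 11.4 also requires explicit documentation of the Visit 1 injection-site findings, so that later reactions can be told apart.

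**What is analysed.** Local tolerability is not among the SAP 3.3.1 safety endpoints, and no part of SAP Section 8 covers it. SAP 8.7 reads: "Other safety assessments include weight, pubertal status, fundoscopy and bone age". The only SAP analysis that names it is in 9.4: "The following analysis will be repeated for US subjects for auto-injection", followed by a list that includes local tolerability.

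**The concern.** The reactions that 11.11.1 screens have already been judged abnormal for a subcutaneous injection. A visible, lasting change that neither limits activity nor is treated would fail both conditions. If a site treats atrophy or a nodule as an injection site reaction, such a case does not become an AE. If another site treats it as a separate diagnosis, it may. An incidence built on mixed practice is hard to interpret.

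This would matter less if the examination and diary findings were tabulated directly, but the SAP plans no such table for the whole population. The primary objective is long-term safety, and auto-injector safety is a secondary objective in the protocol. Local change after years of weekly injection is something this extension should be able to describe with a numerator and a denominator.

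**Working it through.** There is no plan figure to reproduce, so the main check sets the texts side by side.

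**1. Does the 11.11.1 rule cover atrophy and nodules?**
- Pointing to yes: a note in 12.1.1 says that rotating the injection site is expected to lower the risk of atrophy, which ties it to the site. Section 5.3 reports nodules and lipoatrophy directly after injection site reactions.
- Pointing to no: 12.1.1 gives atrophy its own bullet. The same section allows clinically significant examination findings that emerge on treatment to be AEs. Section 12.1.3 requires any change from baseline health that meets the AE definition to be recorded.
- No text says which prevails. For nodules there is no separate bullet at all.

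**2. Does SAP 9.4 have a main analysis to repeat?** Its five auto-injector items compare with the rest of the SAP as follows.

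| Item in 9.4 | Main analysis |
|---|---|
| Exposure/compliance | 8.6 |
| TEAEs | 8.1 |
| Local tolerability | none |
| Antibodies | 8.2 |
| Device PROs | 11.4 |

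The opening of Section 8 commits to tables for the 3.3.1 endpoints, which omit local tolerability, and to listings of all safety evaluations.

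**3. How far could the AE count mislead?** This is an illustration only. Let p be the true proportion of subjects affected and f the share of cases that reach the AE form. Both are assumptions. Then P(no AE reported) = (1 − p·f)^N, with N = 300 (protocol) or 400 (SAP).

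| N | p | f = 1 | f = 0.5 | f = 0.25 | f = 0.1 |
|---|---|---|---|---|---|
| 300 | 1% | 4.9% | 22% | 47% | 74% |
| 300 | 2% | 0.2% | 4.9% | 22% | 55% |
| 400 | 1% | 1.8% | 13.5% | 37% | 67% |

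Example: (1 − 0.01 × 0.25)^300 = 0.9975^300 = 0.47. At f = 0 the probability is 100% for any p.

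A count of 0 in 300 normally gives an exact one-sided 95% upper limit of 1 − 0.05^(1/300) = 0.99%. Here that limit would apply only to cases that were reportable as AEs, not to all cases.

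**4. Do the documents supply an incidence?** Only the phase 2 statement of no nodules or lipoatrophy over 26 weeks, with the predecessor ACP-001. Counting the 12 + 14 + 14 = 40 children on the weekly product, the same limit is 1 − 0.05^(1/40) = 7.2%. Counting all 53 treated, it is 1 − 0.05^(1/53) = 5.5%. Neither rules out the values used in the table.

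**The case against.** A reader might infer more than the text supports, in four ways.

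- *That the protocol excludes lipoatrophy and skin atrophy from the AE data.* It does not say so. Atrophy is listed apart from injection site reactions, 12.1.1 and 12.1.3 leave another route to the AE form, and the Schedule of Events makes examination of injection sites part of AE review. What the text shows is ambiguity.
- *That 11.11 and 11.11.1 contradict each other.* The AE form is to be used only as appropriate, and 11.11.1 can be read as defining when it is.
- *That such changes usually meet neither condition, so the count will be zero.* The documents give no basis for how often they would. Zero is possible but not a necessary result of the rule.
- *That the findings are lost.* They are still collected. Protocol 15.4.1 expects trial-specific data on the eCRF, and SAP Section 5 promises listings of all eCRF data. Auto-injector users also answer questionnaire items on skin marks and injury. Protocol Section 13 describes sponsor review of all trial data, not of AE tables alone.

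All of this stands, and it narrows the point to under-description. It does not remove it. The examination-finding route is permissive and depends on judgement, while 11.11.1 is the specific instruction. Listings give no denominator, rate or time course. The device questionnaire reaches only auto-injector users, at about weeks 6 and 13 after transition. The documents also do not show whether reaction type is recorded on the eCRF.

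A reporting threshold for ordinary injection reactions is a deliberate and defensible choice in a long extension. The criticism is of its unclear edge and of the absent table.

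**Conclusion.** The point holds in two parts. First, 11.11.1 restricts AE reporting of abnormal injection site reactions, and the protocol does not say whether atrophy, lipoatrophy or nodules are included, so the AE tables can under-count them. Second, and independently of how the first is settled, the SAP has no full-population summary of local tolerability, and 9.4 repeats an analysis that is defined nowhere.

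The size of any under-count is unknown. The probabilities above rest on assumed p and f and show only that an AE count of zero would be weak evidence if a material share of cases is not reported. The difference between 300 and 400 planned subjects does not change this. The correction is worth making because the primary objective is long-term safety and the assessments are already performed. It does not call the trial's other safety analyses into question.

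**What to change.** 1. **SAP Section 8.** Add a local tolerability table from the site examinations and diaries, regardless of AE status. Show subjects with any abnormal reaction by visit and at any time, overall and by parent-study group, with the number assessed as denominator. Give atrophy/lipoatrophy and nodules their own rows where type is recorded. For former Genotropin subjects, separate findings present at Visit 1 from new ones. SAP 9.4 can then repeat this table for the auto-injector. If type is not captured, say so and tabulate any abnormal reaction.
2. **Protocol 11.11.1 and 12.1.1.** Reconcile the two so that skin atrophy, lipoatrophy and nodules are classified and recorded the same way at every site. Keep the change to these named findings. A wider criterion, such as any abnormal reaction still present at a visit, would replace the existing threshold during the trial (visits fall about 5 days after a dose) and make AE rates before and after the change hard to compare.

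**Cost.** One table, and a short clarification that needs amendment approval under Protocol 15.9 across about 100 sites. The reported injection-site count may become slightly less favourable. If the amendment is judged not worthwhile, the SAP table alone removes most of the problem, provided the findings are in the database.
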